16.2.3 Imputation methods

16.2.3.1 Multiple Imputation

A linear regression model will be used to perform multiple imputation (MI) under a missing-at-random (MAR) assumption. To help preserve the relationship between outcome and covariates within each treatment a separate model will be run for each treatment. This will also

help ensure that the imputation model does not make stronger assumptions on data relations than the analysis model.

The SAS code below outlines a template for the analysis where covariates and visits can be added or removed as required. To ensure that results can be replicated the data should be sorted by subject number before running the model (the data should be in horizontal format with one subject per dataset row).

```
proc mi data= seed=4572308 n impute=100 out=mi_out;  
by treatment;  
class strata;  
fcs reg (/details);  
var strata weight value1 value2 value3;  
run;
```

Where in the template code the continuous variable to be imputed is *value* (e.g. *value1* could be the baseline value and *value2* the first post-treatment measurement of the variable to be imputed.) Normally, all data collection visits during the analysis period of interest would be included in the model. Including variables using a CLASS statement instead of a BY statement should help facilitate model convergence also when the number of non-missing data points are low for some specific covariate level and visit combination. The FCS option is used to ensure that also non-monotone missing data can be handled in an appropriate way.

If convergence is not obtained the following sequential steps will be used:

1. remove *weight*. If still no convergence, perform step 2
2. remove *status*.

For a situation where several variables need to be imputed using separate models (e.g. using independent models to impute each component needed to derive a response variable *V*) a step-wise process needs to be implemented as outlined below:

1. Run the SAS code as described above for the first variable to be imputed
2. Run the SAS code as described above for the next variable to be imputed (but with the following changes: “data=mi_out”, “out=mi_out2”, “by treatment_imputation_”, “n impute=1”)
3. Repeat step 2, but with input dataset equal to the output dataset from the prior step, until all *j* variables have been imputed resulting in a dataset named *mi_outj*
4. Derive the variable *V* from within *mi_outj*

The required analysis (e.g. ANCOVA) is then performed separately within each imputation dataset (as identified by variable *_imputation_*). To obtain the final result of the imputation process the analysis result from each imputation dataset needs to be combined according to Rubin’s rules as outlined below:

```
ods output parameterestimates=mi_result;  
proc mianalyze data=;
```

```
modeleffects estimate;  
stderr estimate_se;  
run;
```

The *estimate* and *estimate_se* parameters come from the analysis model used to analyze the imputed variable within each imputation dataset (e.g. from the lsmean estimate of the treatment difference and its standard error obtained from PROC LOGISTIC or PROC MIXED.)

To obtain binary response rates and confidence intervals for individual treatment groups the following process should be followed (exemplified for one visit):

```
ods output binomialprop=bin_est;  
proc freq data=;  
by treatment_imputation_;  
table response / binomial (cl=wilson correct);  
run;
```

Then apply a logit transformation on the saved proportions and derive its standard error:

```
data bin_est; set bin_est;  
estimate=log(_bin_/(1-_bin_));  
estimate_se=e_bin/_bin_*(1-_bin_));  
run;
```

The transformed binomial proportion estimates and its standard errors are then combined by applying Rubin's rules as described above using PROC MIANALYZE. Before presenting the combined data it needs to be transformed back as follows:

```
data mi_result; set mi_result;  
prop_est=1/(1+exp(-estimate));  
prop_lower=1/(1+exp(-lclmean));  
prop_upper=1/(1+exp(-uclmean));  
run;
```

If all responses are imputed as 0 (or 1) for all imputation datasets for a specific treatment group then the between-imputation-variation will be zero. The combined final response rate would be presented as seen in any of the imputed datasets but the 95% CI will be undefined.

If after imputation all responses are either 0 or 1 for a combination of treatment group and imputation dataset it will not be possible to perform a logit transformation and the response rate (0% or 100%) will be presented without 95% CI.

16.2.4 Crude incidence and related risk estimates

16.2.4.1 Crude incidence and 100*(1- α)% confidence interval

For n subjects, each at risk to experience a certain event with probability π , the crude incidence is estimated as $p=x/n$, where x is the number of subjects with the event.

Absolute and relative frequencies will be displayed as well as 95% confidence interval for the relative frequency based on the score method including continuity correction ([Newcombe 1998](#)).

With z as $(1-\alpha/2)$ -quantile of the standard normal distribution (SAS: $z=\text{PROBIT}(1-\alpha/2)$), n as total number of subjects (i.e. number of subjects in the denominator), and p as estimated crude incidence (number of subjects with event / n) it is $q=1-p$.

Then the lower limit is

$$L = \max\left(0, \frac{2np + z^2 - 1 - z\sqrt{z^2 + 2 - \frac{1}{n} + 4p(nq+1)}}{2(n+z^2)}\right)$$

and the upper limit is

$$U = \min\left(1, \frac{2np + z^2 + 1 + z\sqrt{z^2 + 2 - \frac{1}{n} + 4p(nq-1)}}{2(n+z^2)}\right).$$

In addition, if $L > p$ then $L = p$ and if $U < p$ then $U = p$.

If appropriate, an exact 100*(1- α)% confidence interval ([Clopper-Pearson 1934](#)) will be obtained by using the SAS procedure PROC FREQ with the EXACT BINOMIAL statement. However, the confidence interval derived via the score method including continuity correction will be the default in safety analyses.

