4. To demonstrate that the efficacy of secukinumab 150 mg s.c. at Week 16 is superior to placebo based on the change from baseline in total Bath Ankylosing Spondylitis Disease Activity Index (BASDAI)
5. To demonstrate that the efficacy of secukinumab 150 mg s.c. at Week 16 is superior to placebo based on the change from baseline in Short Form 36 physical component score (SF-36 PCS)
6. To demonstrate that the efficacy of secukinumab 150 mg s.c. at Week 16 is superior to placebo based on the change from baseline in Ankylosing Spondylitis Quality of Life score (ASQoL)
7. To demonstrate that the efficacy of secukinumab 150 mg s.c. at Week 16 is superior to placebo based on the proportion of subjects achieving an ASAS partial remission
8. Overall safety and tolerability of secukinumab compared to placebo as assessed by vital signs, clinical laboratory values and adverse event monitoring

3 Data presentation

To support China AS submission, tables and figures will be generated for Chinese population and overall separately. Listings will be generated for overall and will be sorted by region (China and non-China), except for the listing of randomization allocation to treatment which will be sorted by the randomization number.

Summary statistics for continuous variables will include N, mean, standard deviation, minimum, lower quartile, median, upper quartile, maximum. Summary statistics for discrete variables will be presented in the number and percent of subjects in each category.

If not otherwise specified, p-values will be presented as two-sided p-values and two-sided confidence intervals will be displayed.

The default level of significance will be set to 5% (two-sided, family-wise type-I-error).

Data analyses will be presented by treatment regimen. Efficacy and safety data for the placebo-controlled period (or the entire treatment period as appropriate) will be presented by the following 2 treatment groups. Subjects may be included in more than one treatment group for some analyses (e.g. exposure-adjusted adverse events over the entire treatment period). The 2 treatment groups represent the regimens subjects will be eligible to be randomized to for the first 16 weeks of the study.

- Secukinumab regimen: secukinumab 150 mg (1 mL, 150 mg/mL) s.c. PFS at BSL, Weeks 1, 2, and 3, followed by administration every four weeks starting at Week 4

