13.1 Adverse events

The crude incidence of treatment emergent adverse events (i.e. events started after the first dose of study treatment or events present prior to the first dose of study treatment but increased in severity based on preferred term and on or before last dose date + 84 days) will be summarized

by primary system organ class and preferred term. Confidence intervals for the crude rate will be derived as described in [Section 16.2.4.1](#). In addition, exposure time-adjusted incidence rates including 95% confidence intervals will be provided for the entire treatment period (see [Section 16.2.5.1](#)). A graphical display of the crude incidence rates and exposure-adjusted rates will be presented for all AEs and serious AEs by system organ class.

Adverse events reported will be presented in descending frequency according to its incidence in the secukinumab group starting from the most common event. Summaries (crude incidences only) will also be presented for AEs by severity and for study treatment related AEs. If a particular AE 'severity' is missing, this variable will be listed as missing and treated as missing in summaries. If a subject reported more than one adverse event with the same preferred term, the adverse event with the greatest severity will be presented. If a subject reported more than one adverse event within the same primary system organ class, the subject will be counted only once with the greatest severity at the system organ class level, where applicable.

Separate summaries will be provided for adverse events suspected to be related to study drug, deaths, serious adverse events, and adverse events leading to discontinuation and adverse events requiring concomitant medication.

Separate summaries will be provided for SAEs and significant AEs that led to treatment discontinuation or dose adjustment or interruption by site in China.

Adverse events will also be reported separately by SMQ according to MedDRA, using a narrow search. The MedDRA version used for reporting the study will be described in a footnote.

A listing of non-treatment emergent adverse events will be provided. These adverse events occurred before the first dose of the study treatment. The crude incidence rate will be provided without treatment information.

For SAEs occurred during screening a listing will be prepared for all subjects screened including screening failures.

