13.6 Compound specific safety evaluation

Safety topics of interest, such as risks defined in the Safety Profiling Plan (SPP), Risk Management Plan or topics of interest regarding signal detection or routine analysis are defined in the Program Case Retrieval Sheet that is stored in CREDI at the path Cabinets/CREDI Projects/A/AIN457A/Integrated Medical Safety.

The crude incidence and exposure-adjusted incidence rates for SPP risks will be summarized. In addition, listings will be provided presenting which subjects experienced which risk.

Important note: For the evaluation of SPP risks primary and secondary system organ classes of the MedDRA dictionary will be considered.

14 Interim analyses

The primary analysis will be performed after all subjects have completed the Week 16 visit in order to support regulatory filing. As the primary analysis is scheduled at Week 16, no adjustments will be made to the testing strategy to control the family-wise type I error. The investigators, site personnel and monitors will continue to remain blinded to the treatment each subject received at randomization all patients have completed the study (Week 60 Follow up) and the final database lock has occurred. Additional analyses may be performed to support interactions with health authorities, as necessary.

15 Determination of sample size

The sample size calculation is driven by the patient exposure requirements in the study population. An overall type I error (2-sided) 5% will be used to control type I error. Secukinumab 150 mg regimen will be tested versus placebo with respect to the primary endpoint (ASAS20 response at Week 16). A sample size of 300 patients in secukinumab 150 mg group and 150 patients in placebo group (randomization ratio = 2:1) is chosen in order to expose 300 patients to secukinumab for safety evaluation and also to achieve adequate power for the primary and secondary endpoints for this study.

Analysis of an unpublished phase III study showed a placebo response rate of about 28.4% and active drug response rate of 61.1% after 16 weeks for ASAS20. Using these assumptions, overall, the power for the ASAS20 endpoint should be about 99% with 300 patients in secukinumab 150 mg group and 150 patients in placebo group based on Fisher's exact test (nQuery Advisor 7.0).

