16.2.2 Analysis of binary and categorical data

16.2.2.1 Summary statistics for binary and categorical data

Summary statistics for discrete variables will be presented in contingency tables and will include count and frequency in each category. If applicable, confidence intervals will be derived as well based on the score method including continuity correction (Newcombe 1998):

With z as $(1-\alpha/2)$ -quantile of the standard normal distribution (SAS: $z=\text{probit}(1-\alpha/2)$, n as total number of subjects (i.e. number of subjects in the denominator), p as estimated crude incidence (number of subjects with event / n) and $q = 1-p$

Then the lower limit is

$$L = 100 \times \max \left(0, \frac{2np + z^2 - 1 - z\sqrt{z^2 + 2 - \frac{1}{n} + 4p(nq+1)}}{2(n+z^2)} \right)$$

and the upper limit is

$$U = 100 \times \min \left(1, \frac{2np + z^2 + 1 + z\sqrt{z^2 + 2 - \frac{1}{n} + 4p(nq-1)}}{2(n+z^2)} \right).$$

In addition, if $L > p$ then $L = p$ and if $U < p$ then $U = p$.

For binary response variables the placebo-adjusted response rates including 95% confidence interval will be derived.

SAS code for risk difference:

```
proc freq data=;
tables response*trt/ riskdiff;
run;
```

Note the response value should be sorted with ‘1’ ahead of ‘0’.

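### The lower limit of the default score interval in the SAP is printed with a sign error, so lower confidence limits for rare events come out too low if programmed as written

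*SAP*

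**What the plan says.** SAP 16.2.4.1 defines the point estimate ("the crude incidence is estimated as $p=x/n$, where x is the number of subjects with the event"), with q = 1 − p, and promises a "95% confidence interval for the relative frequency based on the score method including continuity correction". The limits are printed as:

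- L = max(0, [2np + z² − 1 − z·√(z² + 2 − 1/n + 4p(nq + 1))] / [2(n + z²)])
- U = min(1, [2np + z² + 1 + z·√(z² + 2 − 1/n + 4p(nq − 1))] / [2(n + z²)])

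A truncation rule follows: if L exceeds p, "then $L = p$ and if $U < p$ then $U = p". An exact binomial interval is allowed where appropriate, but "the confidence interval derived via the score method including continuity correction will be the default in safety analyses".

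SAP 13.1 applies this to adverse events: "Confidence intervals for the crude rate will be derived as described in" 16.2.4.1. SAP 16.2.2.1 prints the same two root terms for binary and categorical summaries, where "confidence intervals will be derived as well based on the score method including continuity correction". There both limits are multiplied by 100, while p remains a proportion and the truncation rule is unchanged.

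**The concern.** The two limits of a continuity-corrected score interval come from the same quadratic, with the half-count correction subtracted for the lower limit and added for the upper. The terms under the root that come from the correction should therefore change sign between the limits. The printed formulas switch (nq + 1) to (nq − 1) but keep +2 in both. One of the two limits therefore cannot belong to the named method.

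This is the default interval for crude adverse-event incidences. Safety exposure drove the sample size, and intervals on small event counts are where the lower limit is most distorted in relative terms. A table labelled with this method would show a lower bound that is not that method's bound.

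**Working it through.** **Inputs.** z = 1.95996 (z² = 3.84146), from the two-sided 5% level in SAP 3. Arm sizes are n = 300 and n = 150 (SAP 15). The formulas are those of SAP 16.2.4.1. The SAP gives no worked interval, so there is no plan figure to reproduce.

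**Derivation.** The lower limit P solves p − 1/(2n) − P = z·√(P(1 − P)/n). Put a = np − 1/2, square and collect terms:

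(n + z²)P² − (2a + z²)P + a²/n = 0

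The discriminant is (2a + z²)² − 4(n + z²)a²/n = z²(z² + 4a − 4a²/n). With a = np − 1/2:

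- 4a = 4np − 2
- 4a²/n = 4np² − 4p + 1/n
- z² + 4a − 4a²/n = z² **− 2** − 1/n + 4p(nq + 1)

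For the upper limit a = np + 1/2, and the same steps give z² + 2 − 1/n + 4p(nq − 1), exactly as printed. Only the lower limit is wrong.

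**Check from the SAP alone.** Counting events or non-events must give mirror-image limits: L(x) = 1 − U(n − x). Swapping p and q in the printed upper limit gives z² + 2 − 1/n + 4q(np − 1). Since −4q = −4 + 4p, this equals z² − 2 − 1/n + 4p(nq + 1). Numerically, at n = 300, 1 − U(297) = 0.2586%, while the printed L(3) is 0.0958%.

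**Worked case, 3 events in 300** (p = 0.01, q = 0.99, denominator 2(n + z²) = 607.683, numerator before the root term 6 + 3.8415 − 1 = 8.8415):

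- Printed: the root term is 3.8415 + 2 − 0.0033 + 0.04 × 298 = 17.758, with square root 4.2140. L = (8.8415 − 8.2594)/607.683 = 0.0958%.
- Corrected: the root term is 13.758, with square root 3.7092. L = (8.8415 − 7.2699)/607.683 = 0.2586%.
- Back in the defining equation, the corrected value gives 0.005747 on both sides. The printed value gives 0.007375 on the left and 0.003501 on the right.

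Solving the defining equation numerically at n = 90, 150, 300, 360 and 450 gives the −2 form for every x from 1 to n. The printed form is too low at every one of those counts.

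**Lower 95% limits (%), printed v corrected:**

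| Events | n = 300 printed | n = 300 corrected | n = 150 printed | n = 150 corrected |
|---|---|---|---|---|
| 1 | 0 | 0.017 | 0 | 0.035 |
| 2 | 0 | 0.116 | 0 | 0.231 |
| 3 | 0.096 | 0.259 | 0.195 | 0.518 |
| 5 | 0.482 | 0.615 | 0.969 | 1.234 |
| 15 | 2.844 | 2.926 | 5.730 | 5.897 |
| n/2 | 44.177 | 44.213 | 41.672 | 41.774 |
| n | 98.192 | 98.424 | 96.429 | 96.888 |

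Relative to the corrected limit, the printed one is 100% too low at one or two events, about 62–63% at three, 21–22% at five, 6% at ten and 1% at thirty. In absolute terms the largest gap is at x = n: 0.23 points (n = 300) and 0.46 points (n = 150).

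**Truncation rule.** With −2, the raw lower limit at zero events is slightly above p = 0 (0.030% at n = 300, 0.061% at n = 150), and the rule sets it to 0. With +2, L never exceeds p at either arm size, so that half of the rule does nothing.

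**Units in 16.2.2.1.** Taken literally, 100 × L is compared with p. At n = 300 this triggers the rule for every count from 3 to 300 (298 of 301 possible counts). For 183/300, a lower limit of 55.17 (percent) would be replaced by 0.61.

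**The case against.** The algebra is hard to dispute; the case on the other side is about consequence.

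- **The output is wrong only if the printed expression is coded.** The SAP names the method and cites a source, and the multiple-imputation code in 16.2.3.1 requests the corrected Wilson interval from PROC FREQ by option. This stands as a condition. However, that code carries only the proportion and its standard error into the pooling step, and nothing in the SAP directs the safety tables to the option. The written instruction for them is the formula.
- **The error is small and conservative.** This stands. The upper limit, which bounds how frequent an adverse event could be, is correct. For 2/300 the interval is 0 to 2.65% as printed and 0.12% to 2.65% corrected.
- **No confirmatory inference depends on it.** This stands. Logistic regression, MMRM, the testing sequence, the sample size, the risk differences and the exposure-adjusted rates all use other methods.
- **The idle truncation rule could be just a symmetric partner of the rule for U, which does act at x = n.** Fair: it is supporting evidence only, and the derivation does not need it.
- **A programmer would not code the unit mismatch literally.** Probably true. It is a drafting fault with little practical risk.
- **The sign could be a PDF reading error.** This cannot be fully excluded, but the same +2 appears in both sections, and the neighbouring nq + 1 and nq − 1 are distinguished correctly in each.

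**Conclusion.** The concern holds. The printed lower limit is not that of the continuity-corrected score method, and it is inconsistent with the SAP's own upper limit. If programmed as written, lower limits for crude adverse-event rates and single-group response rates are too low at every count from 1 to n. At zero events the reported limit is 0 either way. The effect is material in relative terms only for rare events: the lower limit is zero up to two events and loses more than half its value at three. It is 0.04 to 0.10 points at mid-range rates and at most 0.46 points at the planned arm sizes.

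This rests on the signs having been read correctly from the PDF and on the planned 300 and 150 patients being the denominators. Efficacy conclusions are unaffected. It should be corrected because it is the stated default for safety tables.

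**What to change.** 1. In SAP 16.2.2.1 and 16.2.4.1, replace z² + 2 with z² − 2 under the root of the lower limit, after confirming the sign in the source PDF. Leave the upper limit as it is.
2. In 16.2.2.1, apply the L > p and U < p rules on the proportion scale and multiply by 100 afterwards.
3. Check the table program against direct solution of the defining equation, and against the corrected Wilson option already named in 16.2.3.1. Test values at n = 300: 0.116% for 2 events, 0.259% for 3 events.

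The cost is one sign in each of two formulas, one sentence and a short program check. No data, analysis set or hypothesis test changes. If tables have already been produced from the printed formula, only the lower limits need to be rerun.

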16.2.4.2 Odds ratio and 100*(1- α)% confidence interval

For an investigational drug group with n_1 subjects at risk, independent from the control group (e.g. placebo or comparator) with n_0 subjects at risk, of whom x_1 and x_0 experience a certain event with probability π_1 and π_0 respectively, the odds ratio is estimated as

$\frac{p_1/(1-p_1)}{p_0/(1-p_0)}$ with $p_1=x_1/n_1$ and $p_0=x_0/n_0$. A conditional exact 100*(1- α)% confidence interval

can be obtained by using the SAS procedure PROC FREQ with statement EXACT OR. However, to be able to adjust for covariates odds ratios will primarily be obtained from PROC LOGISTIC.

16.2.4.3 Risk difference and 100*(1- α)% confidence interval

For an investigational drug group with n_1 subjects at risk, independent from the control group (e.g. placebo or comparator) with n_0 subjects at risk, of whom x_1 and x_0 experience a certain event, the risk difference is estimated as p_1-p_0 with $p_1=x_1/n_1$ and $p_0=x_0/n_0$.

Exact unconditional confidence limits for the risk difference can be obtained with SAS procedure PROC FREQ and option RISKDIFF in the TABLES statement, specifying the RISKDIFF option also in the EXACT statement.

16.2.5 Exposure adjusted incidence rate and related risk estimates

16.2.5.1 Exposure adjusted incidence rate and 100*(1- α)% confidence interval

It will be assumed that for each of n subjects in a clinical trial the time t_j ($j=1, \dots, n$) to the first occurrence of a certain event is observed, or if the event was not experienced, the (censored) time to the end of the observation period. The sequence of first occurrences of an event will be modeled to follow approximately a Poisson process with constant intensity θ . The rate

parameter θ will be estimated as $\lambda=D/T$, where $T = \sum_{j=1}^n t_j$ and D is the number of subjects with

at least one event. Conditionally on T , an exact 100*(1- α)% confidence interval for a Poisson variable with parameter θT and observed value D can be obtained based on (Garwood 1936), from which an exact 100*(1- α)% confidence interval for D/T will be derived as follows (Sahai 1993; Ulm 1990):

$$\text{Lower confidence limit } L = \frac{0.5c_{\alpha/2,2D}}{T} \text{ for } D>0, 0 \text{ otherwise,}$$

$$\text{Upper confidence limit } U = \frac{0.5c_{1-\alpha/2,2D+2}}{T}$$

Where $c_{\alpha,k}$ is the α th quantile of the Chi-square distribution with k degrees of freedom. The example below shows how this should be handled for cases where subjects switch treatment. In particular for summarizing 'Any AIN' as a group, one should take into consideration the sequence of treatments while calculating exposure time for subjects.

[figure not shown]
Table 16-3 Examples for calculating exposure time for incidence rates (IR)

1st treatment / total exposure time	2nd treatment / total exposure time	AE event onset (in days from study start)	Exposure for IR
Placebo / 100 days	AIN457 150 mg / 200 days	Day 50 (during 1st treatment) Day 110 (10 days into 2nd treatment)	Placebo: 50 days AIN457 150 mg: 10 days Any AIN: 10 days

